## 2 CLINICAL PROTOCOL SYNOPSIS

Compound No.
E2020
Name of Active Ingredient
Donepezil hydrochloride
Study Protocol Title
A Multi-Center, Randomized, Double-Blind, Placebo-Controlled, Parallel-Group Study of Donepezil Hydrochloride (E2020) in patients with Dementia Associated with Cerebrovascular Disease
Investigator(s)
TBD
Site(s)
Approximately 25 centers in Korea
Study Period and Phase of Development
From June 2013 to January 2019, Phase 4
Objectives
Co-Primary objectives

• To confirm that donepezil hydrochloride (E2020) has superior efficacy compared with placebo in improving cognitive function, as measured by Alzheimer's Disease Assessment Scale-Cognitive subscale (ADAS-cog), in patients with dementia associated with cerebrovascular disease (VaD).

• To demonstrate that donepezil hydrochloride (E2020) has superior efficacy compared with placebo in improving global function, as measured by Clinician's Interview-Based Impression of Change-plus Caregiver Input (CIBIC-plus), in patients with VaD.

Secondary objectives

• To evaluate the efficacy (as measured by MMSE and executive function test) and safety of E2020 compared with placebo, in patients with VaD.

Study Design
This is a multi-center, randomized, double-blind, placebo-controlled, parallel-group study with an open-label extension. The main part of the study consists of 2 phase; screening phase (SCR; 1 to 4 weeks), and double-blind phase (DB; 24 weeks, placebo-controlled). DB phase includes 2 periods; titration and maintenance. The duration of titration period is 4 weeks. Prior to performing any procedures or evaluation, written informed consent will be obtained. Up to 4 weeks prior to randomization, prospective patients will be screened to confirm their diagnosis and suitability for study entry. Subjects who continue to meet all of the inclusion and none of the exclusion criteria will be randomly assigned to receive either donepezil or placebo. Donepezil or placebo will be taken once daily in the evening for the duration of their participation in the study.

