#### Primary Efficacy Analyses:

The co-primary efficacy variables are used as follows to determine whether donepezil has superior efficacy compared to placebo:

- For ADAS-cog change from baseline to Week 24, an analysis of covariance (ANCOVA) model with baseline (covariate) and treatment (main effect) will be used for testing main effect.
- For CIBIC-plus scores, least squares (LS) mean scores at Week 24 will be compared between groups to demonstrate numerical superiority of donepezil to placebo (the difference is less than 0), using ANCOVA model with CIBIS-plus (covariate) and treatment group (main effect).

For the measurements of each visit and the change from baseline to each visit of both endpoints, descriptive statistics (median, mean, standard deviation (SD), minimum, maximum, and number of patients with non-missing data for both variable; number and percentages of each score for CIBIC-plus) will be presented. Where appropriate, least square (LS) mean, between-treatment difference in least square (LS) means, 95% confidence intervals (CIs) for the difference and p value in each visit will also be presented.

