**Sample Size Rationale**

The primary endpoints are the change from baseline to Week 24 (LOCF) in ADAS-cog and the measurement at Week 24 (LOCF) of the CIBIC-plus.

The estimates of these endpoints were referred from the result of subgroup (MMSE less than 24) in pooled data of previous double blind studies (E2020-A001-307 and E2020-A001-308).

The mean difference and standard deviation of the change from baseline to final visit in ADAS-cog were estimated as  $-2.404 \pm 5.955$ , using pooled data of E2020 groups (5 mg+10 mg). When the significance level was set as 5.0% (two-tailed) and statistical power as 80.0%, the subject number needed to detect statistically significant difference by 2 sample t test was calculated to be 196 (98/arm).

On the other hand, the mean difference and the standard deviation of CIBIC-plus score at the final visit were estimated as  $-0.261 \pm 1.162$ , when CIBIC-plus was regarded as continuous measurement [scored from 1 (marked improvement) to 7 (marked worsening) point]. The subject number needed to reduce the probability that donepezil is inferior to placebo in point estimate to 2.5% or less, was calculated to be 308 (154/arm).

Therefore, the subjects number required to achieve primary objectives simultaneously became 308 (154/arm). In consideration of exclusion from the analysis set (approximately 5%), the sample size was defined as 324 (162/arm).

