# 8 STUDY OBJECTIVES

## 8.1 Co-PRIMARY OBJECTIVE

- 1) To confirm that donepezil hydrochloride (E2020) has superior efficacy compared with placebo in improving cognitive function, as measured by ADAS-cog, in patients with dementia associated with cerebrovascular disease (VaD).

2) To demonstrate that donepezil hydrochloride (E2020) has superior efficacy compared with placebo in improving global function, as measured by CIBIC-plus, in patients with VaD.

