## CO-PRIMARY EFFICACY ANALYSIS

The co-primary efficacy variables are used as follows to determine whether donepezil has superior efficacy compared to placebo:

- For ADAS-cog change from baseline to Week 24, an analysis of covariance (ANCOVA) model with baseline as covariates and treatment as main effect will be used for testing main effect.
- For CIBIC-plus scores, least squares (LS) mean scores at Week 24 will be compared between groups to demonstrate numerical superiority of donepezil to placebo (the

difference is less than 0), using ANCOVA model with CIBIS-plus (covariate) and treatment group (main effect).

For the measurements of each visit and the change from baseline to each visit of both endpoints, descriptive statistics (median, mean, SD, minimum, maximum and number of patients with non-missing data for both variables; number and percentages of each score for CIBIC-plus) will be presented. Where appropriate, least square (LS) mean, between-treatment difference in least square (LS) means, 95% confidence intervals (CIs) for the difference and p value in each visit will also be presented.

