**9.7.2 Determination of Sample Size**

The primary endpoints are the change from baseline to Week 24 (LOCF) in ADAS-cog and the measurement at Week 24 (LOCF) of the CIBIC-plus.

The estimates of these endpoints were referred from the result of subgroup (MMSE less than 24) in pooled data of previous double blind studies (E2020-A001-307 and E2020-A001-308).

The mean difference and standard deviation of the change from baseline to final visit in ADAS-cog were estimated as  $-2.404 \pm 5.955$ , using pooled data of E2020 groups (5 mg+ 10 mg). When the significance level was set as 5.0% (two-tailed) and statistical power as 80.0%, the subject number needed to detect statistically significant difference by 2 sample t test was calculated to be 196 (98/arm).

On the other hand, the mean difference and the standard deviation of CIBIC-plus score at the final visit were estimated as  $-0.261 \pm 1.162$ , when CIBIC-plus was regarded as continuous measurement [scored from 1 (marked improvement) to 7 (marked worsening) point]. The subject number needed to reduce the probability that donepezil is inferior to placebo in point estimate to 2.5% or less, was calculated to be 308 (154/arm)..

Therefore, the subjects number required to achieve primary objectives simultaneously became 308 (154/arm). In consideration of exclusion from the analysis set (approximately 5%), the sample size was defined as 324 (162/arm).

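### The CIBIC-plus co-primary promises superior efficacy but asks only for a point estimate below zero, which a drug with no global effect meets half the time

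*Protocol*

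**What the plan says.** The synopsis and section 8.1 set the second co-primary objective as "To demonstrate that donepezil hydrochloride (E2020) has superior efficacy compared with placebo in improving global function, as measured by CIBIC-plus". The lead-in to the co-primary analysis in section 9.7.1.6 says that the two variables are "used as follows to determine whether donepezil has superior efficacy compared to placebo".

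The two criteria beneath that lead-in differ in kind. ADAS-cog change is tested for a treatment effect by ANCOVA, and all tests are at two-sided 5%. For CIBIC-plus, LS means at Week 24 "will be compared between groups to demonstrate numerical superiority of donepezil to placebo", explained as a difference below 0. The synopsis repeats this. LS-mean differences, 95% CIs and p values by visit are to be presented where suitable, but nothing makes them a condition of success.

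The sample size in section 9.7.2 follows the same rule. The CIBIC-plus number is the one "needed to reduce the probability that donepezil is inferior to placebo in point estimate to 2.5% or less, was calculated to be 308" (154/arm). This exceeds the 196 (98/arm) needed for ADAS-cog and therefore sets the size of the trial.

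**The concern.** A negative sign on a point estimate does not demonstrate superiority, so the claim is stronger than the criterion behind it.

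The exposed case is a drug that helps cognition but not global function. That case is realistic here. Section 7.1.2 reports that Study 319 was significant on ADAS-cog but not on CIBIC-plus, and section 7.2 gives the lack of consistency on CIBIC-plus across the three earlier studies as part of the rationale. If the drug truly has no global effect, the plan as written would still report superior global efficacy in about half of such trials.

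**Working it through.** **Inputs (section 9.7.2).** ADAS-cog: difference −2.404, SD 5.955, two-sided 5%, 80% power. CIBIC-plus: difference −0.261, SD 1.162, wrong-sign probability at most 2.5%. Evaluable 154/arm, randomised 162/arm. The correlation between the two test statistics is not given; 0 to 0.5 is assumed.

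**1. The plan's own figures reproduce.**
- ADAS-cog: a noncentral-t calculation gives 98/arm (97 with the normal approximation), as stated.
- CIBIC-plus, normal: n = 2 × (1.96 × 1.162 / 0.261)² = 152.3, so 153/arm. With the t distribution the wrong-sign probability is 0.0252 at 153/arm and 0.0248 at 154/arm, which gives the stated 154/arm.
- Exclusions: 308 × 1.05 = 323.4, rounded up to 324.

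The sample-size arithmetic is not the problem, and it confirms that the sign rule is the intended criterion.

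**2. The sign rule when CIBIC-plus has no effect.** SE = 1.162 × √(2/154) = 0.1324. At a true difference of 0 the estimate is symmetric about 0, so P(difference < 0) = 0.50 whatever the N or SD.

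**3. Joint success, ADAS-cog as planned and CIBIC-plus null, 154/arm.** The ADAS-cog SE is 5.955 × √(2/154) = 0.679, so the standardised effect is 2.404 / 0.679 = 3.54 and power is Φ(3.54 − 1.96) = 0.943 (0.942 by noncentral t). At correlation 0, joint success is 0.943 × 0.50 = 0.472. Other values are bivariate normal probabilities:

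| Correlation | Sign rule on CIBIC-plus | Two-sided 5% on CIBIC-plus |
|---|---|---|
| 0 | 0.472 | 0.0236 |
| 0.3 | 0.485 | 0.0248 |
| 0.5 | 0.493 | 0.0250 |

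Higher correlations only move the sign-rule figure towards its ceiling of 0.50.

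**4. Joint success when neither endpoint has an effect.** At correlation 0 this is 0.025 × 0.50 = 0.0125; at 0.5 it is 0.0227.

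**5. What a passing result can look like.** The 95% CI half-width is 1.968 × 0.1324 = 0.2606. An observed difference of −0.01 passes the rule with a CI of −0.271 to +0.251.

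**6. What the planned N gives for a real CIBIC-plus test.** Setting the wrong-sign probability at 2.5% places the assumed effect about 1.97 standard errors from zero (0.261 / 0.1324), almost exactly on the 5% critical value. Power is therefore about one half: 0.502 at 154/arm and 0.522 at 162/arm.
- Joint power for both endpoints at 5% is 0.476 to 0.497 at 154/arm.
- Even when the effect is truly −0.261, 1 − 0.502 / 0.976 = 0.486 of the results that pass on sign have a 95% CI that includes 0.
- Going from 98/arm to 154/arm lowers the wrong-sign probability from 5.9% to 2.5%.
- 80% power for CIBIC-plus alone would need about 313/arm evaluable.

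**The case against.** The rule is deliberate and openly stated. The protocol calls the CIBIC-plus criterion numerical, spells it out in both the synopsis and section 9.7.1.6, and sizes the trial on it. The ADAS-cog test must also succeed, so the error when neither endpoint works is small. The 47–49% is conditional on a full cognitive effect and exactly zero global effect; it is not the trial's overall false-positive rate. Section 7.2 reports inconsistency, not absence of effect: in Study 307 the 5 mg group was significant on CIBIC-plus, and in Study 308 both donepezil groups improved more than placebo. A directional criterion is one reasonable response to such a history. The CI and p value would probably be reported, so a reader could judge the result inferentially.

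Much of this stands. The directional rule may be kept, and 47–49% should be read only as the conditional figure it is. But ADAS-cog protects the joint conclusion only when cognition has no effect either; it does not protect the separate claim about global function. The general two-sided 5% sentence does not help, because CIBIC-plus success is defined by the sign of the difference. If a significance test was meant after all, the planned N gives it only about 50% power, and section 9.7.2 could not then say that 308 is enough for both objectives together. Either reading leaves text to correct.

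**Conclusion.** The concern holds. The objective and the lead-in promise demonstrated superiority on CIBIC-plus; the criterion delivers only a direction, met 50% of the time at zero effect. With ADAS-cog at its planned effect, both co-primaries then succeed in 47–49% of trials, against 2.4–2.5% under a two-sided 5% test. This should be fixed because it concerns the conclusion drawn from a co-primary endpoint.

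The 50% figure needs only an estimate that is symmetric about its true value. The joint figures rest on the protocol's effects and SDs, 154/arm, unadjusted comparison of means and an assumed correlation of 0 to 0.5, to which they are not sensitive.

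**What to change.** Keep the sample size and the sign criterion, and change the claim.

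1. In the synopsis, section 8.1, and the lead-in and CIBIC-plus bullet of section 9.7.1.6, describe the CIBIC-plus objective and conclusion as directional consistency (numerical superiority), not as demonstrated superior efficacy.
2. In section 9.7.1.6, require the Week 24 CIBIC-plus LS-mean difference to be reported with its 95% CI in every case. Allow a claim of superior global function only if the two-sided 95% CI lies wholly below 0. This makes two tiers of conclusion, and the text should say so.
3. Preferably, add to the synopsis and section 9.7.2 that the 2.5% is the wrong-sign probability under the assumed −0.261; that the rule is met 50% of the time at zero effect; that a two-sided 5% CIBIC-plus test has about 50% power at 154/arm (52% at 162/arm), with joint power about 48–50% at 154/arm; and that the number above 196 rests on the directional criterion. Items 1 and 2 are the essential part.

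No change to N, visits or data is needed. The cost is a weaker stated claim on global function and an amendment to a co-primary objective, which under section 11.1 may need health-authority submission and IRB/IEC approval. Powering a true CIBIC-plus superiority test at 80% would take about 626 evaluable subjects (313/arm) and is not proposed.

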#### **SECONDARY EFFICACY ANALYSES**

MMSE and executive function test score change from Baseline to Week 24 will be analyzed using a same ANCOVA model as is described for the ADAS-cog. Other statistical inference (estimating and testing) will also be analyzed in the same way with primary analysis.

#### **EXPLORATORY EFFICACY ANALYSES**

Not applicable

#### **9.7.1.7 Pharmacokinetic, Pharmacodynamic, and Pharmacogenomic/Pharmacogenetic Analyses**

Not applicable

#### **9.7.1.8 Safety Analyses**

The evaluation of safety parameters will be conducted on the SAS. The incidence rates for AEs by body system, preferred term, severity, and relationship to study mediation will be calculated. Individual vital signs will be descriptively summarized by treatment group and total of treatment groups and visit. Changes from Baseline to each individual post- baseline visit and to the final visit will be calculated. For clinical laboratory parameters, changes from Baseline to each visit, will be summarized. Shift tables depicting shifts in or out of the normal range, from Baseline to the final study visit, will also be provided.

ECG data will be categorized at Baseline, and results for each subject at the end of treatment will be compared to those at Baseline. Data on other medications used by subjects during the study will be collected and summarized by therapeutic class and generic components.

#### **EXTENT OF EXPOSURE**

Study compliance and the extent of exposure to the study drug for the safety analysis set during the double-blind treatment period will be summarized descriptively.

## ADVERSE EVENTS

The AE verbatim descriptions (investigator terms from the CRF) will be classified into standardized medical terminology using the Medical Dictionary for Regulatory Activities (MedDRA). Adverse events will be coded to the MedDRA (Version 15 or higher) lower level term (LLT) closest to the verbatim term. The linked MedDRA preferred term (PT) and primary system organ class (SOC) are also captured in the database.

A treatment-emergent AE (TEAE) is defined as an AE that emerges during treatment, having been absent at pretreatment (Baseline) or

- Reemerges during treatment, having been present at pretreatment (Baseline) but stopped before treatment, or
- Worsens in severity during treatment relative to the pretreatment state, when the AE is continuous.

Only those AEs that were treatment emergent will be included in summary tables. All AEs, treatment emergent or otherwise, will be presented in subject data listings.

Treatment-emergent AEs (TEAEs) will be summarized by treatment group. The incidence of TEAEs will be reported as the number (percentage) of subjects with TEAEs by SOC and PT. A subject will be counted only once within a SOC and PT, even if the subject experienced more than one TEAE within a specific SOC and PT. The number (percentage) of subjects with TEAEs will also be summarized by maximum severity (mild, moderate, or severe).

The number (percentage) of subjects with TEAEs will also be summarized by relationship to study drug (possibly related, probably related, and not related).

## LABORATORY VALUES

Laboratory results will be summarized using Système International (SI) units, as appropriate. For all quantitative parameters listed in Section 9.5.1.5 Safety Assessments (Laboratory Measurements), the actual value and the change from baseline to each post-baseline visit and to the end of treatment (defined as the last on-treatment value) will be summarized by visit and treatment group using descriptive statistics(median, mean, SD, minimum, maximum and number of patients with non-missing data). Qualitative parameters listed in Section 9.5.1.5 will be summarized using frequencies (number and percentage of subjects), and changes from baseline to each post-baseline visit and to end of treatment will be reported using shift tables. Percentages will be based on the number of subjects with both non-missing baseline and relevant post-baseline results.

Laboratory test results will be assigned a low/normal/high (LNH) classification according to whether the value was below (L), within (N), or above (H) the laboratory parameter's reference range. Within-treatment comparisons for each laboratory parameter will be based on 3-by-3 tables (shift tables) that compare the baseline LNH classification to the LNH classification at each postbaseline visit and at the end of treatment. Similar shift tables will also compare the baseline LNH classification to the LNH classification for the highest and lowest value during the treatment period.

**VITAL SIGNS**

Descriptive statistics for vital signs parameters (i.e., systolic and diastolic blood pressure [BP] [mmHg], pulse [beats per minute], and weight (kg)) and changes from baseline will be presented by visit and treatment group.

**ELECTROCARDIOGRAMS**

For ECG Measurement, Changes from Baseline or Screening to the last visit in the 12-lead ECG during the double-blind phase will be calculated by the incidence of a new or worsening clinically significant finding (treatment emergent ECG measures and physical examination shift table).

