**Safety analysis**

The evaluation of safety parameters will be conducted on the SAS.

The incidence rates for AEs by body system, preferred term, severity, and relationship to study medication will be calculated. Individual vital signs will be descriptively summarized by treatment group and visit. Changes from Baseline to each individual post-baseline visit and to the final visit will be calculated. For clinical laboratory parameters, changes from Baseline to each visit, descriptive statistics (median, mean, standard deviation (SD), minimum, maximum, and number of patients with non-missing data) will be presented. Shift tables depicting shifts in or out of the normal range, from Baseline to the final study visit, will also be provided. ECG data will be categorized at Baseline, and results for each subject at the end of treatment will be compared to those at Baseline. Data on other medications used by subjects during the study will be collected and summarized by therapeutic class and generic components.

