##### **9.1.2.1 Titration Period**

During the Titration period, subjects assigned to donepezil group will be started E2020 on 5 mg/day. On the other hand, subjects assigned to placebo group will be started placebo tablet

matched to 5 mg tablet. The duration of titration period is 4 weeks. The dose will be increased to 10 mg according to investigator's clinical judgment at Week 4 (Day 28-35).

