## ELECTROCARDIOGRAMS

A 12-lead ECG will be performed at Screening and at the Visit 3, 4, 5, 6, 7 and early discontinuation of DB phase, and visit 8, 9 10 and early discontinuation of OLE phase. The ECG

will be a complete, standardized 12-lead recording. Electrocardiograms will be properly mounted and evaluated by the investigator or a qualified consultant.

An ECG abnormality may meet the criteria of an AE as described in this protocol (see Adverse Events and Other Events of Interest [Section 9.5.1.5]) and the CRF Completion Guidelines. In these instances, the AE corresponding to the ECG abnormality will be recorded on the Adverse Events CRF.

For ECG abnormalities meeting criteria of an SAE (see Serious Adverse Events and Other Events of Interest [Section 9.5.1.5]), the site must fax or email the SAE report including the ECG report to the sponsor using the SAE form (see Reporting of Serious Adverse Events [Section 9.5.4.1]).

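### The ECG safety summary looks only at the last visit, so for a completer four of the five on-treatment ECGs do not enter it

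*Protocol*

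**What the plan says.** **Collection.** Section 9.5.1.5 (Electrocardiograms) states: "A 12-lead ECG will be performed at Screening and at the Visit 3, 4, 5, 6, 7 and early discontinuation of DB phase". Table 2 agrees. It places Visits 3 to 7 at Weeks 4, 6, 12, 18 and 24 and shows no ECG at Visit 2 (Week 0).

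**Analysis.** The ECG comparison is described in three places:

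- Synopsis, Safety analysis: "results for each subject at the end of treatment will be compared to those at Baseline".
- Section 9.7.1.8, opening text: "ECG data will be categorized at Baseline, and results for each subject at the end of treatment will be compared to those at Baseline".
- Section 9.7.1.8, Electrocardiograms: "Changes from Baseline or Screening to the last visit in the 12-lead ECG during the double-blind phase will be calculated", and this is to be done "by the incidence of a new or worsening clinically significant finding (treatment emergent ECG measures and physical examination shift table".

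**Other safety measures.** In the same section, laboratory values are summarised at each post-baseline visit and at the end of treatment, and in addition "Similar shift tables will also compare the baseline LNH classification to the LNH classification for the highest and lowest value during the treatment period". For vital signs, values and changes are presented by visit. The heading for other safety analyses is marked not applicable, and Section 9.7.1.9 plans no other analyses.

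**The concern.** Safety is part of the secondary objective, and exclusion criteria 8 and 9 (conduction disorders, prolonged QT/QTc, life-threatening arrhythmia) show that the sponsor regards cardiac rhythm and conduction as relevant in this population. The dose is raised on "clinical judgment at Week 4 (Day 28-35"), so the ECGs at Weeks 6, 12 and 18 are the ones recorded after escalation and before the final visit. An analysis confined to the last visit describes only what is still present at the end. It cannot show how many subjects had a clinically significant ECG change during treatment, which is what an incidence of treatment-emergent findings is normally taken to mean.

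Two wording faults sit in the same text. The synopsis and Section 9.7.1.8 use Baseline as the ECG reference, although no ECG is scheduled at the Baseline visit. The ECG paragraph also calls for a physical examination shift table, although neither Table 2 nor Table 3 schedules a physical examination.

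**Working it through.** The plan states no figure to reproduce. The check is a count of scheduled ECGs against those that enter the stated comparison, followed by a comparison of the analysis rules.

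**1. ECGs per completer (Section 9.5.1.5, Table 2)**

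- On-treatment ECGs: Weeks 4, 6, 12, 18, 24 = 5.
- Used in the stated comparison: Week 24 = 1.
- Not in the ECG summary: 5 − 1 = 4 (Weeks 4, 6, 12, 18), or 4/5 = 80%.
- Of these four, after the Week 4 dose-increase visit: Weeks 6, 12, 18 = 3.

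A subject who stops early has fewer ECGs, and again only the last one counts.

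**2. Scale**

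If all 324 randomised subjects completed, which is an upper bound:

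- Scheduled on-treatment ECGs: 324 × 5 = 1,620.
- In the comparison: 324 × 1 = 324.
- Outside it: 1,620 − 324 = 1,296, and 1,296/1,620 = 80%.

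These are tracings, not subjects with findings.

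**3. Analysis rules side by side (Section 9.7.1.8)**

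| Measure | By visit | End of treatment or last visit | Extreme on treatment |
|---|---|---|---|
| Laboratory values | yes | yes | yes (highest and lowest) |
| Vital signs | yes | yes (final visit) | not stated |
| ECG | not stated | yes | not stated |

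Of these three repeatedly measured quantities, only ECG is confined to the final assessment. No reason is given.

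**4. What happens to a transient finding**

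Take a clinically significant abnormality first seen at Week 6 and absent at Week 24.

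- ECG summary: Screening against last visit gives no change.
- Adverse-event tables: it is counted if it was recorded as an adverse event, and not otherwise.
- If it led to dose reduction, it must have been an adverse event. Sections 9.1.2.2 and 9.4.1 allow reduction in the double-blind phase only for an adverse event whose causal link to the drug is not excluded.
- If it was present when the subject withdrew, the early-discontinuation ECG is the last one and can capture it.

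The gap is therefore a finding that resolved before the last visit and was not recorded as an adverse event.

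**5. Open-label extension**

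Section 9.7.1.10 applies the double-blind safety methods. ECGs are scheduled at Visits 8, 9 and 10, so for a completer 3 − 1 = 2 of the three fall outside the summary in the same way.

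**The case against.** **The adverse-event tables already catch these findings.** This stands in part. The general definition in Section 9.5.1.5 covers any unfavourable sign, all observed adverse events must be reported, and treatment-emergent events are tabulated by arm, severity and relationship. A reader might infer that a transient finding after escalation vanishes from the safety analysis. The documents do not support that, and for a finding that led to dose reduction they show the opposite. The route still does not replace an ECG summary. The ECG section says only that an abnormality may qualify as an adverse event, which is a case-by-case judgment. The one adverse-event criterion that names ECG concerns measurements the protocol does not require, whereas these are required. The protocol does not rely on adverse events alone for laboratory values either.

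**The ECG paragraph speaks of incidence and of treatment-emergent measures, which could mean at any time.** That reading is possible taken alone. However, the sentence attaches the incidence to the change to the last visit, and the synopsis and the opening of Section 9.7.1.8 both say end of treatment. If any-time incidence is meant, the three statements need to be brought into line.

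**By-visit and worst-case tables are matters for the statistical analysis plan.** Such a plan could add them without contradicting the protocol. The point is that the protocol does not leave the comparison open: it fixes one in three places. A plan that followed this text exactly would carry the limitation forward.

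**The output is descriptive.** This is true. No hypothesis test, sample size or co-primary conclusion depends on it, and that limits the weight of the point.

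**Conclusion.** The point holds for the ECG summary. As written, it uses one of five on-treatment ECGs for each completer. Three of the four omitted follow the Week 4 dose-increase visit. A clinically significant finding that resolves before the last visit is shown as no change. The count rests only on the visit schedule; the figure of 1,296 of 1,620 tracings also assumes full completion.

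Three stronger readings are not supported:

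- The omitted ECGs are not unused in the trial. They are evaluated when taken and can give rise to adverse events. They are absent from the ECG summary.
- It cannot be said that the comparison between arms is biased toward no difference. That would need an excess of transient findings on donepezil that also escape adverse-event recording, and the protocol gives no figure for either.
- A chance of one in five of capturing a finding would require assuming that it appears at a single, randomly placed visit. Nothing in the protocol supports that.

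This is a worthwhile correction to a descriptive safety analysis. It does not threaten the efficacy conclusions.

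**What to change.** In the synopsis (Safety analysis) and in both places in Section 9.7.1.8:

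1. Define the main ECG summary as the number and percentage of subjects per arm with a clinically significant finding, new or worse than at Screening, at any post-baseline double-blind ECG. Include unscheduled and early-discontinuation tracings.
2. Add shift tables by arm from Screening to each visit and to the worst on-treatment category, in line with the laboratory section.
3. Keep the last-visit comparison as an additional row.
4. Name Screening as the reference, since no ECG is scheduled at Visit 2.
5. Delete the physical examination shift table.

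Section 9.7.1.10 then carries the change into the open-label extension without a separate rule.

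The cost is revised wording and a few more descriptive tables. The ECGs are already scheduled and evaluated, so no procedure or visit is added.
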